3. OBJECTIVES

3.1. Primary objective

- To estimate the incidence of CMV secondary infections in seropositive adolescent females.

3.2. Secondary objectives

- To estimate the incidence of CMV primary infections in seronegative adolescent females.

3.3. Tertiary objectives

- To develop assays that allow the differentiation of CMV secondary infections caused either by reinfection or by re-activation, in CMV seropositive adolescent females.
- To assess the diagnostic value of different assays to evaluate seroconversion in blood and the detection of CMV DNA in different body fluids.
- To describe the proportion of secondary infection caused either by re-infection or re-activation.
- To collect samples for immunological and biological disease-related exploratory assays.
- To explore socio-demographic or behavioral factors associated with CMV infection.
- In case of pregnancies, to document the birth prevalence of CMV congenital infections.
- To evaluate the concordance between screening testing data at local laboratories (or alternatively, central laboratories) and the GSK Biologicals or designated laboratory testing data.

4. ENDPOINTS

4.1. Primary endpoints

- Occurrence of CMV secondary infections determined in all seropositive subjects on samples collected during the 4-month Site Visits until study conclusion:
 - Anti-CMV tegument protein IgG antibody concentration in serum (ELISA).
 - Number of CMV DNA copies (pp65 or other genes) in urine (qPCR).

4.2. Secondary endpoints

- Occurrence of CMV primary infection determined in all seronegative subjects on samples collected during the 4-month Site Visits until study conclusion:
 - Anti-CMV tegument protein IgG antibody concentration in serum (ELISA).

4.3. Tertiary endpoints

- Further characterization of primary and /or secondary CMV infections in a subset of subjects on selected samples of the Sample Collection Visits*.
 - Number of CMV DNA copies (pp65 or other genes) in urine (qPCR).
 - Number of CMV DNA copies (pp65 or other genes) in saliva (qPCR).

* In case of a positive sample at a 4-month Site Visit time point, testing will be done on selected samples collected during the Sample Collection Visit. The selection of samples to be tested will be based on the qPCR results obtained following the Site visits.

- Further characterization of primary and /or secondary CMV infections in a subset of subjects on all available samples of the 4-month Site Visits:
 - Anti-CMV tegument protein IgG antibody avidity index in serum (ELISA).
 - Anti-gB IgG antibody avidity index in serum (ELISA).
 - Anti-gB IgG antibody concentration in serum (ELISA).
 - Anti-CMV IgM antibody concentration in serum (ELISA).
 - Number of CMV DNA copies (pp65 or other genes) in saliva, blood (qPCR).
 - Assessment of anti-CMV neutralizing antibodies on different target cells and/or other virus strains.
- Development of assays that will allow differentiating re-infection from re-activation from primary infection in a subset of subjects
 - Characterization of CMV strains by genotyping/sequencing.
 - Exploring the CMV strain specific antibody profile using peptide microarrays.
- Assessment of the expression of host genes* using techniques such as qPCR or mRNA microarray in a subset of subjects

* excluding genes related to hereditary characteristics of the subject.

- Evaluation of the impact of demographic, social or behavioral factors upon CMV infection.
- Occurrence of congenital CMV infection in newborns of subjects who become pregnant during the study:
 - Evidence of CMV DNA in urine and/or saliva of newborns within 10 days of delivery by using qPCR (pp65 or other genes).

5. ANALYSIS SETS

5.1. All Enrolled Set (“Total cohort” in protocol)

All screened subjects who provide informed consent and provide demographic and/or other baseline screening measurements, regardless of the subject’s randomization and vaccination status in the trial, and receive a subject ID.

Demography and baseline characteristics tables as well as subject listings will be produced on the All Enrolled Set.

5.2. Per Protocol Set (PPS) (“ATP cohort” in protocol)

All subjects in the All Enrolled Set who:

- Have serology results available.
- Have no major protocol deviations leading to exclusion
- Are not excluded due to other reasons

5.3. Other Analysis Sets

All subjects in the All Enrolled Set who consent to provide exploratory assay data at relevant time points will be included in an exploratory assay subset. Subgroup analysis sets will be included based on two-fold and four-fold increases in anti-CMV tegument protein IgG antibodies in serum among CMV seropositive subjects. The analyses of the tertiary endpoints will be detailed in a separate statistical analysis plan.

5.4. Criteria for eliminating data from ATP

Elimination codes are used to identify subjects to be eliminated from analysis. Detail is provided below for each set.

Elimination from According to Protocol (ATP)

Code 900 (invalid informed consent or fraud data) will be used for identifying subjects eliminated from PPS.

5.4.1.1. Excluded subjects

A subject will be excluded from the ATP analysis under the following conditions

Code	Condition under which the code is used
1040	Administration of concomitant vaccine(s) forbidden in the protocol (see also eligibility criteria)

	CDM responsibility from review of individual data listings
2010	Protocol violation linked to the inclusion/exclusion criteria including age and excluding codes mentioned below.
2040	Administration of any medication forbidden by the protocol Responsibility of CRDL following review of individual data listings
2050	Underlying medical condition forbidden by the protocol Responsibility of CRDL following review of individual data listings
2070	Concomitant infection not related to the vaccine which may influence immune response Responsibility of CRDL following review of individual data listings
2090	Blood samples taken but: non-compliance with blood sampling schedules (dates of BS not corresponding to adapted protocol intervals or unknown BS)
	When a visit and/or a vaccination and/or a blood sample is Not Done/Performed, only the code 2100 is attributed to the subject.
2100	Serological results not available (including lost samples, blood sample not done, unable to test, absence of parallelism). elimination code if ALL are missing
2500	Other: For seropositive subjects only: Serological results not available for anti-CMV tegument protein IgG at the 4 site visits (Visit 1 to Visit 4) and from at least 2 sample collection visits during Year 1
3500	Urine and saliva samples taken but: non-compliance with blood sampling schedules (dates of BS not corresponding to adapted protocol intervals or unknown BS)

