7.2. Subject withdrawal

Subjects who are withdrawn because of SAE must be clearly distinguished from subjects who are withdrawn for other reasons. Investigators will follow subjects who are withdrawn as result of a SAE until resolution of the event (see Section [6.3](#)).

From an analysis perspective, a ‘withdrawal’ from the study refers to any subject who did not come back for the concluding visit foreseen in the protocol.

All data collected until the date of withdrawal/last contact of the subject will be used for the analysis.

A subject is considered a ‘withdrawal’ from the study when no study procedure has occurred, no follow-up has been performed and no further information has been collected for this subject from the date of withdrawal/last contact.

Investigators will make an attempt to contact those subjects who do not return for scheduled visits or follow-up.

Information relative to the withdrawal will be documented in the eCRF. The investigator will document whether the decision to withdraw a subject from the study was made by the subject herself, by the subject’s parent(s) or LAR(s), or by the investigator, as well as which of the following possible reasons was responsible for withdrawal:

- SAE.
- Protocol violation (specify).
- Consent withdrawal, not due to an adverse event.
- Moved from the study area.
- Lost to follow-up.
- Death.
- Other (specify).

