8.4.2. According-to-protocol cohort (amended 19 February 2015)

The **according-to-protocol (ATP) cohort** will include all subjects who meet all inclusion criteria and no exclusion criteria for the study, who do not have any elimination criteria during the study (Section 5.5.2.9) and who comply with the study procedures.

A detailed, comprehensive list of reasons for elimination from ATP analyses will be established at the time of data cleaning.

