8.7. Statistical methods

Statistical analyses will be described in detail in a separate document, the statistical analysis plan (SAP).

The primary analysis will be performed on the ATP cohort(s). Analysis on the Total cohort may be performed to complement the primary analysis. **(Amended 19 February 2015)**

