5.5. Important protocol deviation not leading to elimination from per-protocol analysis set

The following important protocol deviations will be reported by groups:

- Short follow-up: subjects who missed one or more of the site visits and sample collection visits.

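### SAP elimination code 2500, for seropositive subjects only, does not say whether one missing Year 1 IgG result or all four trigger exclusion; the only reading with real content conflicts with the SAP's own rules for missed visits

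*SAP*

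**What the plan says.** The elimination table in SAP 5.4.1.1 defines code 2500 as "Other: For seropositive subjects only: Serological results not available for anti-CMV tegument protein IgG at the 4 site visits (Visit 1 to Visit 4", and the sentence goes on "and from at least 2 sample collection visits during Year 1". No word such as any or all qualifies the four visits, and S- subjects have no matching code. Codes in this table exclude the subject, not the affected visit.

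Four other provisions deal with missing visits:

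- Code 2100, for missing serology in either group, is an "elimination code if ALL are missing".
- A note in the same table reads "When a visit and/or a vaccination and/or a blood sample is Not Done/Performed, only the code 2100 is attributed to the subject".
- SAP 5.5 lists, among deviations that do not lead to elimination, "Short follow-up: subjects who missed one or more of the site visits and sample collection visits".
- SAP 6.2.1 measures an IgG rise from the last available value when a visit was missed or its serology is unavailable.

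In the protocol, section 7.2 says "All data collected until the date of withdrawal/last contact of the subject will be used for the analysis". Section 8.4.2 limits the ATP cohort to subjects "who do not have any elimination criteria during the study (Section 5.5.2.9) and who comply with the study procedures" and does not separate S+ from S-. Section 8.7 says "The primary analysis will be performed on the ATP cohort(s). Analysis on the Total cohort may be performed to complement the primary analysis". SAP 5.1 assigns only demography, baseline tables and listings to the All Enrolled Set.

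**The concern.** Code 2500 governs who enters the primary analysis of the primary objective, and it cannot be programmed from its text. If one missing result eliminates, an S+ girl with a four-fold IgG rise at Month 4 who moves away at Month 10 leaves the primary set together with her event and her urine DNA results. An S- girl with the same visits stays. Year 1 secondary infections would then be counted only among girls with complete results to Month 12, which is selection on attendance after baseline. The primary and secondary incidences would also rest on different follow-up rules. The SAP assigns no outcome analysis to the All Enrolled Set that would recover the excluded data.

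The second clause has a separate defect. It asks for serology from Sample Collection Visits, but protocol 3.1 and Table 5 show that those visits collect only urine and saliva.

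**Working it through.** **1. The plan's own figures (protocol 8.2).** Expected events: 200 × 0.02 × 3 = 12, as stated. Enrolment: 200/0.85 = 235.3, so 236; 200/0.80 = 250. The stated 240 lies in that range, and 240 × 0.85 = 204, 240 × 0.80 = 192. Both figures reproduce.

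**2. The rules applied to one case.** Take a subject with results at Visits 1 and 2 who withdraws before Visit 4, with no other code applying.

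| Rule | S+ | S- |
|---|---|---|
| Code 2500, any result missing | removed | not applicable |
| Code 2500, all four missing | stays | not applicable |
| Code 2100 | stays | stays |
| Note on visits or samples not done (only 2100) | stays | stays |
| SAP 5.5 | stays, reported | stays, reported |

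The any-missing reading is the only line that removes her.

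**3. Which reading has content.** Protocol section 3 bases the analysis serostatus on the sponsor's or designated laboratory's result, and Table 2 ties it to Visit 1. An analysed S+ subject therefore already has Visit 1 serology, so all four can hardly be missing, and code 2100 already covers complete absence. All-missing makes code 2500 nearly redundant, so any-missing is the working reading.

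**4. Cost of early withdrawal under any-missing.** Inputs: 240 S+ and about 160 S- (protocol Table 1), 15-20% drop-out over 3 years and 2% per year (protocol 8.2). The documents do not give the timing of drop-out, so a constant hazard is assumed.

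- Leaving by Month 12: 1 − 0.85^(1/3) = 5.27%; 1 − 0.80^(1/3) = 7.17%.
- S+ removed: 240 × 5.27% = 12.7; 240 × 7.17% = 17.2. Remaining: 227 and 223.
- S- leaving over the same period and kept: 160 × 5.27% = 8.4; 160 × 7.17% = 11.5.
- Hazard λ = −ln(0.85)/3 = 0.0542 or −ln(0.80)/3 = 0.0744 per year. Total S+ person-years: 240 × 0.15/0.0542 ≈ 665; 240 × 0.20/0.0744 ≈ 645.
- Year 1 leavers contribute on average just under half a year: 6.3 and 8.5 person-years, or 0.9% and 1.3% of the total.
- Expected events lost: 6.3 × 0.02 = 0.13; 8.5 × 0.02 = 0.17.
- Upper bound, with all drop-out in Year 1 at a mean of 0.5 year: 36-48 subjects, 18-24 person-years, 0.36-0.48 events.

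**5. Cost of single missing results under any-missing.** The documents give no per-visit missingness. Assume a rate m, independent across visits and of withdrawal. S+ remaining = 240 × (1 − d)^(1/3) × (1 − m)^k, where d is the 3-year drop-out and k is the number of visits at risk.

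| m | k = 4 (Visits 1-4) | k = 3 (Visits 2-4, Visit 1 present) |
|---|---|---|
| 2% | 206-210 | 210-214 |
| 5% | 181-185 | 191-195 |
| 10% | 146-149 | 162-166 |

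The k = 3 column fits better with serostatus requiring a Visit 1 result; k = 4 is the more pessimistic. At 5%, both fall below 200.

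**6. All-missing reading.** No subject with a Visit 1 result is removed, and every cost above is zero.

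**The case against.** The strongest reply is that the SAP may not remove these subjects at all. A girl who has moved away has Visit 4 not done. The note on visits not done then gives her only code 2100, which does not eliminate someone with Visit 1 serology, and SAP 5.5 agrees. This stands as far as it goes: removal is not established. It does not rescue the row. The note could be read as settling only the choice between codes 2090 and 2100, and it speaks of visits or samples not done, whereas code 2500 speaks of results not available, which could include untestable samples. If the note does govern, little is left for code 2500 to do.

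The reply on protocol 7.2 also stands. That section names no cohort, and protocol 8.4.2 already restricts the ATP cohort to subjects who comply with procedures. A reader might infer a flat contradiction; the documents support only a tension.

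The 12 expected events are counted on 200 evaluable subjects after drop-out, so early leavers contribute none of them and their removal takes nothing off that figure. That stands. For the same reason, the 200 is not a like-for-like benchmark for the counts in step 5, which still include girls who leave after Month 12.

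No comparison of S+ with S- is an objective, and SAP section 7 calls all analyses descriptive. The asymmetry therefore affects how the two incidences are read, not a test. S- subjects can still be lost through codes such as 2090 or 3500.

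The row resembles a Year 1 attendance rule that Amendment 2 deleted. That is background only; differing from superseded text is not an error.

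**Conclusion.** Code 2500 is ambiguous, applies to S+ only, and cannot be reconciled with the rest of the SAP on the one reading that gives it real content. The firm conflicts are with SAP 5.5, the note on code 2100 and the last-available-value rule in SAP 6.2.1. The clause on Sample Collection Visits asks for serology that those visits do not produce.

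A reader might conclude that the SAP definitely discards every early S+ withdrawer, or that the primary estimate loses many events that way. The documents do not support either. Removal depends on the any-missing reading. Even then, withdrawal alone costs about 13-17 of 240 subjects, about 1% of person-years and under 0.2 expected events (under 0.5 if all drop-out fell in Year 1). The larger risk is single missing results among girls who stay: at an assumed 5% per visit, 181-185 remain, or 191-195 if only Visits 2-4 are at risk. Those counts rest on a missingness rate that the documents do not give. The reason to act is selection on later attendance in the primary set and a rule that cannot be programmed, more than the withdrawal numbers.

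**What to change.** Delete the whole code 2500 row. Removing only its Visit 1-4 condition would leave a requirement for serology from visits that take no blood; read literally, that could eliminate every S+ subject. Let code 2100 and SAP 5.5 govern missing visits in both S+ and S-, and let each otherwise eligible subject contribute all evaluable Site Visit results up to withdrawal or last contact.

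If the sponsor wants to keep a Year 1 completeness rule, the SAP must state any or all, say how the rule ranks against the code 2100 note and SAP 5.5, drop the serology requirement at Sample Collection Visits, and either apply the rule to both groups or justify the difference.

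The cost is one row of the elimination table and no new data. The downside is that the per-protocol set will include subjects with short follow-up, which SAP 5.5 already plans to report.

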3. STUDY DESIGN OVERVIEW

Time point							
	Year 1						
Month	M0	M2	M4	M6	M8	M10	M12
Site Visits	V1		V2		V3		V4
Sample Collection Visits		SCV1		SCV2		SCV3	
	Year 2						
Month		M14	M16	M18	M20	M22	M24
Site Visits			V5		V6		V7
Sample Collection Visits		SCV4		SCV5		SCV6	
	Year 3						
Month		M26	M28	M30	M32	M34	M36
Site Visits			V8		V9		V10
Sample Collection Visits		SCV7		SCV8		SCV9	
Samples:							
Blood	✓		✓		✓		✓
Saliva	✓	✓	✓	✓	✓	✓	✓
Urine	✓	✓	✓	✓	✓	✓	✓

In case of pregnancy resulting in live birth: Urine and or saliva from the newborn (please refer to [Table 3](#)) will be collected (if possible) as per standard of care in the center where the subject has delivered or through a home visiting nurse or alternatively, the subject may be asked to come back to the study center within 10 days of delivery.

- **Type of design:** Prospective, multi-center, multi-country study.
- **Study Design:**
 - 10 scheduled **Site Visits** approximately every 4 months.
 - 9 **Sample Collection Visits**, approximately at mid-term between 2 Site Visits (i.e. approximately 2 months after a Site Visit) where samples will be collected either through self-collection by the subjects, by a home-visiting nurse or through a new visit at the study center.
- **Study population:** Adolescent females aged between 10 and 17 years regardless of CMV status.
- **Number of subjects and study groups:**

At Visit 1, subjects will be enrolled regardless of their seropositivity status. Subjects will be allocated to the CMV seropositive (S+) or the CMV seronegative (S-) groups based on the local laboratory results (alternatively, a GSK designated and validated central laboratory can perform the analyses). Enrolment will be terminated when approximately 240 CMV seropositive females have been enrolled.

- CMV Seropositive Group (S+): Subjects defined as CMV seropositive based on the local laboratory results (or alternatively based on central laboratory results) obtained from the sample collected at Visit 1.
- CMV Seronegative Group (S-): Subjects defined as CMV seronegative based on the local laboratory results (or alternatively based on central laboratory results) obtained from the sample collected at Visit 1.

For statistical analysis, the serostatus will be based on the laboratory results obtained at the GSK Biologicals or designated laboratory.

- **Controls:** Uncontrolled.
- **Type of study:** Self-contained.
- **Data collection:** Electronic Case Report Form (eCRF).

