- **Duration of the study:**
 - Participant: Approximately 36 months.
 - Newborn (in case of pregnancy): Approximately 10 days.

Epoch 001: Prospective data collection starting at Visit 1 (Month 0) and ending at Visit 10 (Month 36).

Table 1 Study groups foreseen in the study

Study Groups	Number of subjects	Age (Min/Max)
S+	+/- 240 seropositive subjects	10 – 17 years
S-	Estimated approximate number of seronegative subjects ⁽¹⁾ : 160	10 – 17 years

⁽¹⁾As subjects will be enrolled consecutively without previous CMV screening with a target number of 240 seropositive subjects, the number of seronegative subjects enrolled will depend on the seroprevalence of the participating countries.

- **Time points and biological samples**
 - Blood: approximately every 4 months;
 - Saliva and urine: approximately every 2 months;
 - Urine and /or saliva of newborn (in case of pregnancy): within 10 days post-delivery.

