3.1. Discussion of study design

The study sites will be selected in multiple countries, including countries where the CMV prevalence is assumed to be high in order to enroll primarily CMV seropositive adolescent females to allow the evaluation of CMV secondary infections. Since enrolment will proceed without previous CMV screening, some of the enrolled subjects will be seronegative. The enrolled seronegative subjects will allow the estimation of the incidence of CMV primary infections in the adolescent population.

To increase the probability to capture all CMV infections (primary and secondary infections), regular sample collection time-points have been arranged:

- **Site Visits:** Subjects will be asked to perform a Site Visit approximately every 4 months for 3 years (10 Site Visits in total). At Site Visits, blood, urine and saliva will be collected.
- **Sample Collection Visits:** Subjects will be contacted to perform urine and saliva sample collections at home either by self-collection or by a home visiting nurse. Alternatively subjects may be asked to come back to the study center where the investigator or designate will collect the samples. These Sample

Collection Visits will occur approximately every 4 months for 3 years between 2 Site Visits (9 Sample Collection Visits in total).

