5.6.2. Biological samples

Each sample will be collected from all subjects.

Table 5 Biological samples (amended 19 February 2015)

Sample type	Quantity	Time point	Priority rank
Blood for humoral immunity determination	Approximately 10 mL	Months 0, 4, 8, 12, 16, 20, 24, 28, 32 and 36	1
Blood for molecular biology	Approximately 4 mL	Months 0, 4, 8, 12, 16, 20, 24, 28, 32 and 36	1
Blood for gene signature expression (RNA transcript)	Approximately 2.5 mL	Months 0, and 12*	2
Urine	Approximately 10 mL	Months 0, 2, 4, 6, 8, 10, 12, 14, 16, 18, 20, 22, 24, 26, 28, 30, 32, 34 and 36	1
Saliva	NA	Months 0, 2, 4, 6, 8, 10, 12, 14, 16, 18, 20, 22, 24, 26, 28, 30, 32, 34 and 36	1

* Blood samples will be collected until approval of protocol amendment 2.

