6.2. Objectives

6.2.1. Analysis of primary objective

Descriptive statistics will be provided for each primary endpoint at all available time-points and will include (not exhaustive) the following tabulations (with 95% confidence interval [CI]):

- The percentage of CMV seropositive subjects with increase of anti-CMV tegument protein IgG antibodies in serum. An increase will be defined by both a 2-fold or greater increase *and* separately a 4-fold or greater increase in the anti-tegument antibody concentration between subject visits or the last available anti-tegument antibody value if the subject missed a visit or serological results are unavailable.
- The percentage of CMV seropositive subjects with appearance or increase of CMV DNA in urine. A reactivation/reinfection event, based on DNA in the urine, will be defined as any one of the following : (1) the appearance of any detectable CMV DNA by PCR in a sample if CMV DNA was not detected in the previous sample for that subject (2) if the previous sample had CMV DNA detected, but was below the LLOQ for the assay, any value above the LLOQ will be considered a reactivation/reinfection event; and (3) if the previous sample result was above the LLOQ, an increase $\geq 0.5 \log_{10}$ CMV DNA copies/mL in the subsequent sample will be considered an event. It is expected that CMV-positive subjects may have more than one reactivation/reinfection event during the follow up period in this study.

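### SAP code 2500 ties elimination from the primary set to IgG results from sample collection visits, which take no blood, and does not say whether all or any Year-1 results must be missing

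*SAP*

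**What the plan says.** Protocol 8.7 puts the primary analysis on the ATP cohort, which SAP 5.2 calls the Per Protocol Set. SAP 5.4.1.1 lists the conditions that exclude a subject from it. Code 2500, for seropositive subjects only, concerns anti-tegument IgG results that are not available "at the 4 site visits (Visit 1 to Visit 4) and from at least 2 sample collection visits during Year 1".

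Neighbouring text bears on the same subjects:

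- **Code 2100** covers unavailable serology, including lost and untestable samples, with the qualifier "elimination code if ALL are missing".
- **A note between codes 2090 and 2100** reads "When a visit and/or a vaccination and/or a blood sample is Not Done/Performed, only the code 2100 is attributed to the subject".
- **SAP 5.5** reports missed site or sample collection visits as a deviation that does not lead to elimination.
- **SAP 6.2.1** measures an IgG rise between visits, "or the last available anti-tegument antibody value if the subject missed a visit or serological results are unavailable".

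On sampling, Protocol 3 has "Blood: approximately every 4 months", and Protocol 5.6.2 (Table 5) gives the months for humoral-immunity blood as "Months 0, 4, 8, 12, 16, 20, 24, 28, 32 and 36". For the visits in between, Protocol 3.1 says "Subjects will be contacted to perform urine and saliva sample collections at home", with a nurse visit or a return to the centre as alternatives.

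**The concern.** The row asks about a result that the study does not generate. Sample collection visits fall at Months 2, 6 and 10 of Year 1, and none is a blood time point. Protocol Table 8 runs the tegument IgG assay on serum at Visits 1 to 10 and lists only CMV DNA, in a subset, for sample collection visits. Amendment 1 removed IgG testing in saliva. The limb therefore cannot tell one subject from another.

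What is left is a test on Visits 1 to 4 with no quantifier. Two programmers could both follow the text and report different denominators for the secondary-infection percentages, in the population of the primary objective. The stricter version would also drop a subject's whole 36 months because of one Year-1 result, although the endpoint runs to Month 36 and SAP 6.2.1 can bridge the gap.

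**Working it through.** **The plan's own figures.** Protocol 8.2 expects about 12 infected among 200 evaluable subjects: 200 × 0.02 × 3 = 12. From 240 enrolled, drop-out of 15–20% leaves 240 × 0.85 = 204 to 240 × 0.80 = 192, consistent with about 200.

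**Logic of the row.** IgG results from Year-1 sample collection visits: 0 of 3 for every subject. Take every pattern of IgG availability at Visits 1–4 (2⁴ = 16) and of urine/saliva collection at the three sample collection visits (2³ = 8), giving 16 × 8 = 128. These are unweighted counts of patterns, not probabilities.

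| Reading of code 2500 | Patterns eliminated |
|---|---|
| Removal: all of V1–V4 missing, and at least 2 collection visits without IgG (always true) | 1 × 8 = 8 |
| The same, restricted to the 64 patterns with Visit 1 present | 0 |
| Removal: any of V1–V4 missing, and at least 2 collection visits without IgG (always true) | 15 × 8 = 120 |
| Retention: IgG needed at V1–V4 and at 2 or more collection visits | 128 |
| Retention: IgG at V1–V4, with urine/saliva at 2 or more collection visits | 128 − 1 × 4 = 124 |

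The restricted row matters because of Protocol 3: "For statistical analysis, the serostatus will be based on the laboratory results obtained at the GSK Biologicals or designated laboratory". Footnote 3 to the SAP's table of study procedures says the same for Visit 1. I take that result to be the tegument IgG, the only antibody assay planned for all subjects in Protocol Table 6. A subject classed seropositive then has a Visit 1 result by definition.

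**Size of the *any missing* reading, note applied.** Visits or samples not done receive only code 2100, so only lost or untestable samples at V2–V4 count. The documents give no loss rate. Assume 1–2% per sample, independent, so the usable fraction p is 0.99 or 0.98.

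- 240 × (1 − 0.99³) = 240 × 0.0297 = 7.1
- 240 × (1 − 0.98³) = 240 × 0.0588 = 14.1

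**If the note does not reach code 2500.** Visit 4 is one third of the way through follow-up. At a constant drop-out rate:

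- 240 × (1 − 0.85^(1/3)) = 12.7
- 240 × (1 − 0.80^(1/3)) = 17.2

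The two sources overlap slightly. Together they give 240 × (1 − 0.9473 × 0.9703) = 19.4 and 240 × (1 − 0.9283 × 0.9412) = 30.3. Missed visits by subjects who stay in would add to this.

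**If the limb was meant as urine/saliva samples.** The chance of fewer than 2 usable of 3 is 1 − (3p²(1 − p) + p³), which is 0.07 or 0.28 subjects in 240. If failing either limb eliminates, 7.2 or 14.4 are removed. If both must fail, 0.002 or 0.017 are. The row would still need to say which.

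**Effect on events.** At 6% over three years, losing 7.1 or 14.1 subjects costs 0.43 or 0.85 infected subjects. This is a scale only. Protocol 8.2 words its 2% as re-infection, whereas SAP 6.2.1 also counts reactivation.

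**The case against.** The row can be run. It sits in a list of conditions for exclusion and is phrased as results not available, so a removal condition is the natural form. In that form the impossible limb is merely idle. Three other provisions favour the lenient quantifier: SAP 5.5 does not eliminate for missed visits, code 2100 requires all results to be missing, and SAP 6.2.1 uses the last available value. Under that quantifier nobody is removed. The analyses are descriptive (SAP 7), and Protocol 8.4.2 leaves the detailed elimination list to data cleaning.

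Most of this stands, and it limits the point. A reader might infer that the rule cannot be executed, or that it empties the seropositive set. The documents do not support either as the working interpretation. Removing all 240 requires recasting an exclusion condition as a retention requirement, which also clashes with SAP 5.5. A reader might also infer that the serostatus in the row is undefined; the two passages on the analysis laboratory answer that.

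What the objection does not settle is a lost or untestable sample. SAP 5.5 covers missed visits only. Code 2500 is a separate ground from code 2100 and may lawfully be stricter, so the two are not in contradiction. The lenient reading makes code 2500 a rule that can never fire, which is hard to accept as its purpose. Nor can one simply assume that urine and saliva were meant: code 3500 names those samples explicitly, and code 2500 names IgG. A superseded Year-1 cohort definition, shown in Protocol Appendix C under Amendment 2, asked for samples rather than serology from two such visits. It may be the source of the wording, but it is no longer in force and does not define the current rule.

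**Conclusion.** The point holds as a defect in one row of the current SAP. The sample-collection-visit limb refers to results that cannot exist and separates no subjects. The remaining test on Visits 1 to 4 lacks a quantifier. Under the removal form, the outcome is 0 of 240 (all missing), about 7 to 14 (any missing, note applied), or about 19 to 30 (any missing, note not applied, with drop-out before Visit 4).

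These counts rest on an assumed 1–2% independent sample loss and a constant drop-out rate, neither of which the documents give. Even the *any missing* count with the note applied costs less than one expected infected subject at the protocol's rate. The case for correction is that the primary denominator should be determined by the text, and that the strict reading discards usable follow-up. It is not that the estimates would move much. It should be fixed.

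**What to change.** In SAP 5.4.1.1, delete from code 2500 both the sample-collection-visit serology condition and the Year-1 all-visits test. Leave missing serology to code 2100, SAP 5.5 and SAP 6.2.1.

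Add one sentence to SAP 6.2.1: the IgG-rise percentages use subjects with a Visit 1 IgG result from the GSK or designated laboratory and at least one later Site Visit IgG result, while urine DNA results stay in for all subjects in the set. This needs no new cohort. SAP Annex 1 (10.2) already leaves subjects with missing measurements out of each immunogenicity analysis, and the sentence makes that explicit for an endpoint that needs two values. It concerns about 4 to 6 subjects who leave before Visit 2: 240 × (1 − 0.85^(1/9)) = 4.3 and 240 × (1 − 0.80^(1/9)) = 5.9, at a constant rate over nine 4-month intervals.

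If Year-1 completeness is of interest, define it as IgG at Site Visits and urine/saliva at sample collection visits, say *all* or *any*, and present it as a labelled sensitivity analysis.

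The cost is one table row and one sentence, with no new data. The downside is that slightly more subjects with incomplete Year-1 serology stay in the primary set.
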